# 9.5 Device Interrogation

Details apply to all subjects in Phases I and II.

There are no required routine device interrogations for this study because data will be available through home communicator uploads to LATITUDE. However, if device interrogation using a home communicator is not possible (e.g during extended hospitalization), sites will be notified when the data must be manually obtained through one of two methods of device interrogation: using a Consult or using a programmer. If a programmer interrogation is used, the "device data dump" (not "save all to disk") option should be chosen. If data are stored on a disc or flash drive, the disc or flash drive should be kept in the subject's MANAGE-HF study binder at the investigative site, and copy should be mailed to the sponsor.

# 9.6 Alert Monitoring Center

Details apply to all subjects in Phases I and II.

The AMC is operated by Boston Scientific staff that is trained to provide technical support of all commercial pacemaker and defibrillator devices. They also provide support for the LATITUDE patient management system. The AMC does not provide any site monitoring; site monitoring is detailed in Section 16.

During Phases I and II of the MANAGE-HF study, the AMC will provide support to clinical sites. The AMC will not practice medicine or provide any independent medical recommendations for patients. While the AMC will be blinded to study endpoint data, they will have access to metrics related to integration of HeartLogic into the clinic, and may provide advice in the form of best practices.

Study investigators will also be provided with a HeartLogic Alert Management guide (Section 9.4.2).

# 9.7 Posture Sensor Calibration

Details apply to all subjects in Phases I and II.

Posture sensor calibrations are attempted by the clinician and patient using the programmer application at baseline and again at every annual follow-up visit. Calibration should be performed using the two-position method for increased accuracy. This requires the patient to sit and to lie down, so the calibration must be conducted in a room with adequate facilities. Once the patient is in position, the clinician will run the software on the programmer for the data collection. It takes approximately 10 seconds of data collection for each position. The entire procedure should take about 1-2 minutes.

There may be instances where the posture sensor is unable to be calibrated. This occurs because the sensor is still initializing, or collecting data, and has not yet reached a state in which it can be calibrated. If the calibration is attempted and unsuccessful, the participant does not need to be brought back for an additional visit with the only purpose of attempting the calibration again. However, the calibration may be attempted at the next scheduled visit.

**Important:** The device will NOT collect any Sleep Incline data until a body calibration has been performed. Thus, an attempt to calibrate the posture sensor is a required step at the baseline and every annual in-clinic follow-up visit. If the calibration is unsuccessful, the attempt and reason for lack of success should be documented.

#### 9.8 Randomization Crossovers (Phase II only)

In Phase II, crossing over from one randomized group to the other group (from HeartLogic Alerts OFF to ON or vice versa) is not allowed.

#### 9.9 Study Completion

Phase I will be complete after the final Phase I subject has been followed for 12 months, or upon recommendation from the Steering Committee. Phase II will be complete after the required number of primary endpoint events has been accrued, or until a futility point has been reached. The study will be complete after Phase II has concluded.

Upon completion of each phase, sites will be notified that the phase has ended and instructed to exit subjects from actively followed in the applicable phase. No additional follow-up visits will occur in the phase, and no additional adverse event reporting will occur once the phase has finished. Subjects will continue to be followed as determined by their health care professional, but not as a part of the clinical trial.

If the study fails to meet the pre-specified primary endpoint, HeartLogic may be turned off if there are patient safety concerns. Importantly, turning off HeartLogic does not affect any other performance aspect of the device.

#### 9.10 Source Documents

Details apply to both phases (Phases I and II) of the MANAGE-HF study.

Source documents are "printed, optical or electronic document containing source data", the source data being "all information in original records… necessary for the reconstruction and evaluation of the clinical investigation".

Source documentation is required during this study. The participating investigator must maintain original source documents that are accurate, complete, and current related to the subject's participation in this study. Source documentation must include but is not limited to:

- Medical record verification that subject meets Inclusion and Exclusion Criteria
- Completed patient informed consent
- Patient medical file with all required study data elements
- Prescribed cardiovascular and heart failure medications
- Documentation of adverse events, including hospitalizations
- Printed copies of HeartLogic sensors/alerts and LATITUDE data

Table 9-3. Source Documentation Requirements		
Requirement	Disposition	
Screening form	Retain at center	
Informed consent form	Retain at center	
Demographic data	Retain at center	
HeartLogic Sensors and Alert	Retain at center	
Programming		
Medications	Retain at center	
Heart failure assessment	Retain at center	
NT-proBNP	Retain at center	
NYHA classification	Retain at center	
KCCQ and EQ-5D-5L	Retain at center	
Treatment documentation	Retain at center	
Device data assessment	Retain at center	
Adverse events	Retain at center	
Weight and blood pressure	Retain at center	
Protocol deviations	Retain at center	
Hospitalizaion	Retain at center and send a copy to BSC	
Death Information	Retain at center and send a copy to BSC	
Subject Randomization	Electronic Data Capture system	

Table 9-5: Source Documentation Requirements

Abbreviations: NYHA: New York Heart Association; KCCQ: Kansas City Cardiomyopathy Questionnaire; AMC: Alert monitoring center

# **10** Study Endpoints and Statistical Considerations

All analyses described in this section apply to subjects randomized in Phase II. No data from subjects enrolled in Phase I will contribute data to any endpoint analyses.

#### **10.1 Primary Endpoint**

The primary endpoint of the MANAGE-HF trial will assess the freedom from all-cause mortality and heart failure hospitalizations, as adjudicated the Clinical Events Committee (CEC, described in Section 20.3). The primary endpoint will compare randomized HeartLogic and Control groups and be assessed using data collected following randomization in Phase II of MANAGE-HF.

10.1.1 Hypothesis for Primary Endpoint

The following set of hypotheses will be evaluated for the primary endpoint:

H0: The risk of mortality and heart failure hospitalization for the HeartLogic group will be greater than or equal to the risk for the control group

HA: The risk of mortality and heart failure hospitalization for the HeartLogic group will be less than the risk for the control group

10.1.2 Sample Size for Primary Endpoint

The sample size required for Phase II of MANAGE-HF is event-driven. Between 1500 and 2500 subjects will be enrolled in the trial to accrue the necessary number of endpoint events to sufficiently power the primary endpoint. Final sample size will be determined during the study using a sample size re-estimation interim analysis. The assumptions used to calculate the sample size are described in a separate MANAGE-HF Statistical Analysis Plan.

10.1.3 Statistical Methods for Primary Endpoint

The methods used to evaluate the Primary Endpoint are described in a separate MANAGE-HF Statistical Analysis Plan.

#### **10.2** Secondary Endpoints

Descriptions of the Secondary Endpoints and associated data evaluated are described in the following sections. The statistical methods used to evaluate the Secondary Endpoints are described in a separate MANAGE-HF Statistical Analysis Plan.

10.2.1 Secondary Endpoint 1: Freedom from all-cause mortality

Survival (freedom from all-cause mortality) between the randomized groups will be assessed, including all deaths occurring during Phase II of the trial.

10.2.2 Secondary Endpoint 2: Freedom from heart failure hospitalizations (time-to-first event)

Freedom from a heart failure hospitalization will be evaluated and compared between the randomized groups. Each subject's first heart failure hospitalization will contribute to the endpoint. Data observed during Phase II of the trial will be included in the analysis.

10.2.3 Secondary Endpoint 3: Risk of multiple heart failure hospitalizations

Multiple heart failure hospitalizations will be evaluated and compared between the randomized groups. All heart failure hospitalizations for each subject will contribute to the endpoint. Data observed during Phase II of the trial will be included in the analysis.

10.2.4 Secondary Endpoint 4: Change in NYHA Classification

Change in NYHA from baseline through 12 months will be evaluated and compared between the randomized groups. Data observed during Phase II of the trial will be included in the analysis.

10.2.5 Secondary Endpoint 5: Change in Quality of Life

Change in Quality of Life from baseline through 12 months will be evaluated and compared between the randomized groups. Data observed during Phase II of the trial will be included in the analysis.

10.2.6 Secondary Endpoint 6: Change in NT-proBNP

Change in NT-proBNP from baseline through 12 months will be evaluated and compared between the randomized groups. Data observed during Phase II of the trial will be included in the analysis.

10.2.7 Secondary Endpoint 7: Change in Medication Status

Change in medication status from baseline through 12 months will be evaluated and compared between the randomized groups. Data observed during Phase II of the trial will be included in the analysis.

#### 10.3 General Statistical Methods

All sample size calculations were performed and all statistical analyses will be done with SAS version 9.3 or higher.

10.3.1 Study Success Criteria

The study will be considered successful if the null hypothesis for the primary endpoint is rejected.

#### 10.3.2 Analysis Sets

All primary and secondary endpoint analyses will be performed following intention-to-treat (ITT) methodology, in which each subject is analyzed per their intended (i.e., randomized) treatment assignment. An as-treated analysis will be performed as well, in which subjects would be analyzed per the treatment received and may be time-varying to accommodate cross-overs. A per-protocol analysis will also be performed.

#### 10.3.3 Control of Systematic Error Bias

Selection of subjects for enrollment in both phases will be made from the Investigator's usual subject load. All subjects meeting the eligibility criteria and having signed the ICF will be eligible for enrollment in the study.

To reduce the possible introduction of selection bias, subjects in Phase II will be randomized to their treatment assignment. To reduce the possible introduction of observer bias, deaths and heart failure hospitalizations will be adjudicated by an independent Clinical Events Committee (CEC).

#### 10.3.4 Control of Type-I Error

Overall Type I error for the primary endpoint will not exceed one-sided 2.5%. Type I error will be split and managed for the interim superiority analyses by employing an O'Brien-Fleming-type error spending function.

Secondary endpoints and other sensitivity analyses will be performed at the nominal one-sided 2.5% and will not be adjusted for the interim primary endpoint analyses.

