## 4 Study Objectives

There are two objectives of the MANAGE-HF multi-phase study :

- Phase I: To evaluate and optimize HeartLogic clinical integration and alert management process.
- Phase II: To evaluate HeartLogic in regards to patient outcomes of death and heart failure hospitalizations. Additionally, Phase II will fulfill regulatory requirements of post-approval study for HeartLogic.

Phase II of the MANAGE-HF trial will begin following completion of Phase I. Subjects enrolled in Phase I will be ineligible to enroll in Phase II.

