#### 6.3 Justification for the Study Design

The multi-phase nature of MANAGE-HF is required to evaluate the multiple objectives of the trial. The use of a single arm in Phase I was chosen as the most appropriate and efficient

design to evaluate and optimize HeartLogic clinical integration and alert management process. Learnings from Phase I will be incorporated into Phase II and reflected in a separate statistical analysis plan that will be approved by Boston Scientific and the FDA. The use of a randomized controlled design in Phase II was chosen to minimize bias in the findings, and is to the gold-standard to demonstrate a true treatment effect.

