#### 10.3.6.1 Sequential Stopping Rules

Interim analyses will be performed during Phase II to assess the superiority of HeartLogic. Five analyses (four interim analyses and one final) are planned. Futility analyses will also be performed at each interim analysis. The Type I error/alpha spending will be managed using an O'Brien-Fleming-type error spending function. The alpha will maintained at an overall one-sided level of 2.5%.

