# **22** Publication Policy

Details in this section apply to both phases (Phases I and II) of the MANAGE-HF study.

BSC requires disclosure of its involvement as a sponsor or financial supporter in any publication or presentation relating to a BSC study or its results. BSC will submit study results for publication (regardless of study outcome) following the conclusion or termination of the study. Boston Scientific Corporation adheres to the contributorship criteria set forth in the Uniform Requirements of the International Committee of Medical Journal Editors (ICMJE; http://www.icmje.org). In order to ensure the public disclosure of study results in a timely manner, while maintaining an unbiased presentation of study outcomes, BSC personnel may assist authors and investigators in publication preparation provided the following guidelines are followed.

All authorship and contributorship requirements as described above must be followed. BSC involvement in the publication preparation and the BSC Publication Policy should be discussed with the Coordinating Principal Investigator(s) and/or Executive/Steering Committee at the onset of the project.

The First and Senior authors are the primary drivers of decisions regarding publication content, review, approval, and submission.

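### Does testing the secondary endpoints at an unadjusted one-sided 2.5%, without saying what may be claimed from them, leave a gap that needs a change?

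*Combined protocol and SAP*

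**What the plan says.** Section 10.3.4 holds the overall Type I error of the primary endpoint at one-sided 2.5%, using an O'Brien-Fleming-type spending function. It then says that secondary endpoints and other sensitivity analyses "will be performed at the nominal one-sided 2.5% and will not be adjusted for the interim primary endpoint analyses".

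Section 10.3.1 defines success by the primary alone: "The study will be considered successful if the null hypothesis for the primary endpoint is rejected".

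Section 10.2 lists seven secondaries: mortality, first heart failure hospitalization, multiple heart failure hospitalizations, and 12-month changes in NYHA class, quality of life, NT-proBNP and medication status. On method it says: "The statistical methods used to evaluate the Secondary Endpoints are described in a separate MANAGE-HF Statistical Analysis Plan". Section 6.3 says that what is learned in Phase I will be "reflected in a separate statistical analysis plan that will be approved by Boston Scientific and the FDA". That SAP is a separate document and was not available for this review.

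On interim looks, Section 10.3.6.1 says: "Five analyses (four interim analyses and one final) are planned". It does not give their timing.

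**The concern.** Section 10.3.4 gives the secondaries a test level but no inferential status. A stated level invites a pass/fail reading. The only adjustment the sentence disclaims is the one for interim looks; it is silent on the fact that seven endpoints are tested.

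The worry is sharpest for the parts of the composite. The Phase II objective in Section 4 is "To evaluate HeartLogic in regards to patient outcomes of death and heart failure hospitalizations", and outside the composite those outcomes are assessed only by secondaries 1 to 3. Section 22 commits to publication whatever the result: "BSC will submit study results for publication (regardless of study outcome) following the conclusion or termination of the study". If the composite failed and mortality alone fell below 2.5%, nothing in the protocol text would stop that result being presented as a test that was met.

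**Working it through.** **Inputs.** From the protocol: one-sided 2.5% for the primary with O'Brien-Fleming-type spending (Section 10.3.4); five analyses (Section 10.3.6.1); seven secondaries (Section 10.2), each at nominal one-sided 2.5%. Assumed, because the protocol does not give them: equally spaced looks, a common correlation between all endpoints, and each secondary read at the look where the trial stops.

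**Step 1: the plan's own figure.** The spending function is α(t) = 2[1 − Φ(z/√t)], with z the 98.75th percentile of the normal distribution. At t = 0.2, 0.4, 0.6, 0.8 and 1 the cumulative spend is 0.0000005, 0.0004, 0.0038, 0.0122 and 0.0250. The Z bounds are about 4.88, 3.36, 2.68, 2.29 and 2.03. Simulated overall error is 2.5%, so the primary's design is coherent. Nothing done with the secondaries alters it.

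**Step 2: seven unadjusted secondaries when nothing works.** If they were independent and tested once, the chance of at least one result below 2.5% is 1 − 0.975^7 = 0.162. With five looks, reading the secondaries at the stopping look against 1.96:

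| Common correlation | At least one of seven | Same, given a failed primary | Counted only if the primary is rejected |
|---|---|---|---|
| 0 | 16.3% | 16.3% | 0.4% |
| 0.3 | 13.8% | 13.0% | 1.1% |
| 0.5 | 11.7% | 10.3% | 1.6% |
| 0.7 | 9.1% | 7.3% | 2.0% |
| 0.9 | 5.9% | 3.6% | 2.4% |

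**Step 3: what a gate on the primary would buy.** The last column above looks like a cure, but it applies only when the primary is also null. Suppose instead that the primary works (drift 3.24, power 89%) while all seven secondaries are null. Then the gate is usually open. The chance of at least one false secondary result after a primary win is about 14% at correlation 0, 14% at 0.3, 13% at 0.5, 10% at 0.7 and 7% at 0.9. A gate alone therefore does not deal with multiplicity; an ordering or an alpha-splitting rule such as Holm would have to be added.

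**Step 4: ignoring the interim looks for one secondary.** Reading a single null secondary at 1.96 at the stopping look gives at most about 2.8% at correlation 0.4, 3.1% at 0.7 and 3.4% at 0.9, against 2.5%. The excess is 0.3 to 0.9 percentage points.

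**Step 5: the cost of formal control.** Take a secondary with 80% fixed-sample power, correlation 0.4 with the primary, and 89% power for the primary. Its power is 70% as planned, 64% with a gate, and 44% with a gate and an O'Brien-Fleming-type boundary. The boundary accounts for 64 − 44 = 20 of the 70 − 44 = 26 points lost, and at that correlation it removes about 0.3 points of excess error.

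**Step 6: does Section 10.3.4 shut out a rule in the SAP?** Section 10.3.4 does not mention the SAP, whereas Sections 10.1.2, 10.1.3 and 10.2 do (for the primary: "The methods used to evaluate the Primary Endpoint are described in a separate MANAGE-HF Statistical Analysis Plan"). That silence proves little. Section 10.3.6.1 is silent too, yet Section 21.1.1 says the primary stopping rule is defined in the SAP. Nor does the flat 2.5% conflict with a testing order: a fixed sequence after the primary tests each hypothesis at the full one-sided 2.5%, which fits the sentence as written. Only a procedure that splits alpha would need to be reconciled with it.

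**The case for a change.** The case for a change is that Section 10.3.4 is the protocol's own statement on Type I error, that it gives a level without a status, and that one or two sentences, written before Phase II data exist, would settle the matter without subjects, alpha or primary power. Mortality and heart failure hospitalization are named in the objective, so a striking result on either would get attention whatever the primary showed.

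Part of this stands. No sentence in the protocol says that the secondaries are supportive, and the 6% to 16% in Step 2 is a fair measure of the risk if someone treated all seven as confirmatory. The rest is weaker. No section plans a claim from a secondary, and the publication commitment is one of transparency, not evidence of an intended claim. The low-cost remedy would write down what the wording already suggests. The stronger remedies, either barring the word 'significant' even after a primary win or imposing a gated procedure, are choices on which reasonable statisticians differ, and Steps 3 and 5 show that they are neither complete nor free.

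**Conclusion.** No change is needed. If the plan is followed as written, the primary result and the declaration of success are sound: the primary's 2.5% is controlled and no secondary can rescue a failed primary. Calling the secondary level nominal, and setting the secondaries beside sensitivity analyses, tells an analyst to treat them as supportive. A trial statistician would report nominal p-values with confidence intervals and would not present a lone mortality result after a failed composite as confirmed.

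The exposure is about 6% to 16% for at least one of seven null secondaries, or about 4% to 16% given a failed primary, and it matters only if those results are promoted to claims. These figures rest on assumed correlations from 0.9 to 0 and equal look spacing. The remaining uncertainty is the SAP: it may already state the rule, and its absence from the documents reviewed cannot be counted as a defect. If the sponsor does intend formal secondary claims, that document is the natural place for an ordering or multiplicity procedure covering all seven.

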#### 10.3.5 Number of Subjects per Investigative Site

To avoid any center effect and bias, one center will not be authorized to enroll more than 20 subjects in Phase I and 100 subjects in Phase II for this study, without approval from Boston Scientific.

#### 10.3.6 Interim Analyses

Analyses of adverse events and device deficiencies will occur at frequent intervals during the course of the study. Results of these analyses will be reviewed by an independent Data Monitoring Committee (DMC) and the Boston Scientific Medical Safety Group to evaluate the safety of the subjects under study. Information about the group sequential stopping rules and interim sample size re-estimation are found in the following sections.

#### 10.3.6.1 Sequential Stopping Rules

Interim analyses will be performed during Phase II to assess the superiority of HeartLogic. Five analyses (four interim analyses and one final) are planned. Futility analyses will also be performed at each interim analysis. The Type I error/alpha spending will be managed using an O'Brien-Fleming-type error spending function. The alpha will maintained at an overall one-sided level of 2.5%.

